7.4 Subject Recruitment and Screening

Patients scheduled to present or presenting to the Lenox Hill Ambulatory Care CCTA Clinic for evaluation of coronary stenosis with the provisional diagnosis of chest pain or angina will be offered the opportunity to participate in this clinical trial. If possible, patients will be contacted in advance of the visit by the study coordinator and educated on the study. All eligible patients will receive education about the study and offered the opportunity to participate upon arrival to the clinic.

The study coordinator, cardiology fellow, or cardiologist will take the patient's medical history as it relates coronary stenting, CABG and other cardiac risk factors (including smoking, family history of heart disease, hyperlipidemia, diabetes, hypertension.) Routine preparation for CCTA will be conducted by clinic staff. As part of this activity patient height and weight will be obtained, and a blood draw for Serum Creatinine to calculate patient eGFR will be taken.

In order to assess the primary endpoint of comparison of event rates for patients treated with CCTA and FFR-CT, we will perform a retrospective chart review of Invasive Coronary Angiograms performed at Lenox Hill Hospital from 2014 to 2018. We will specifically review Cardiac Catheterization reports to screen patients and record data for cases where the indication for Catheterization was (1) Positive stress test and/or (2) Positive CCTA. Based on the catheterization report we will determine whether the patient had obstructive coronary artery disease with/without flow limitation, in the same manner and following the same definitions as those used to categorize level of obstruction in subjects enrolled in the prospective cohort of the study.

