14.2 Statistical Methods

Statistical Aims

1. *To determine the sensitivity, specificity, positive predictive value (PPV) and negative predictive value (NPV) of the CCTA test (with or without stress MPI, as specified in Figure 1) + CT-FFR evaluation to identify chest pain patients with flow-limiting obstructive CAD. The ICA test will be used as gold standard.*
2. *To determine inter-observer reliability of CCTA and CCTA+CT-FFR test readings between an experienced and a non-experienced reader, and compare the results between CCTA and CCTA+CT-FFR; to determine the intra-observer reliability of CCTA and CCTA-FFR reading, for both the experienced and non-experienced reader, and for each reader compare the results between CCTA and CCTA+CT-FFR.*

3. To identify factors of return visit within 90 days in patients who had no ICA test or a negative ICA test result.

Outcome Variables

- *CCTA+CT-FFR test status (Positive/Negative). The test is deemed positive if ICA is required and negative if ICA is not required (see Figure 1).*
- *ICA (gold standard) test status (Positive / Negative). ICA is deemed positive if $FFR < 0.8$ and vessel diameter $>= 2\text{mm}$ or if the patient requires revascularizations based on invasively estimated stenosis severity. It is deemed negative otherwise.*
- *Return visit within 90 days (Y/N). Return visit is defined as patients who return for unplanned cardiac care, including emergency room visits, emergency hospital admissions, urgent percutaneous coronary intervention, coronary artery bypass graft, or acute myocardial infarction. Descriptive statistics (n, mean, median, standard deviation, IQR, frequencies and percentages) will be used to describe the demographic and clinical characteristics of the whole sample.*

For Aim 1, sensitivity, specificity, PPV, and NPV will be computed using the ICA result as the ‘true’ flow-limiting obstructive CAD status and the CCTA+CT-FFR test result as the ‘test’ status. Exact binomial 95% confidence intervals will be computed.

For Aim 2, inter- and intra-observer reliability for the CCTA and CCTA+CT-FFR tests will be assessed using Cohen’s Kappa coefficient. Dependent Kappa coefficients will be compared using a method developed by Donner et al .

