For Aim 3, a survival analysis regression model will be carried out to determine which risk factors are associated with “time-to-return visit”. Proposed factors will include age, sex, race, diabetes, hyperlipidemia, hypertension, active smoking and smoking history, family history of premature heart disease, obesity, and the number of cardiac risk factors present. In addition we will consider adding whether the admission was surgical or medical, and the MS or AP DRG case weight as a measure of severity.

Statistical Methods

Descriptive statistics (n, mean, median, standard deviation, IQR, frequencies and percentages) will be used to describe the demographic and clinical characteristics of the whole sample.

For Aim 1, sensitivity, specificity, PPV, and NPV will be computed using the ICA result as the ‘true’ flow-limiting obstructive CAD status and the CCTA+CT-FFR test result as the ‘test’ status. Exact binomial 95% confidence intervals will be computed.

For Aim 2, inter- and intra-observer reliability for the CCTA and CCTA+CT-FFR tests will be assessed using Cohen’s Kappa coefficient. Dependent Kappa coefficients will be compared using a method developed by Donner et al .

For Aim 3, a survival analysis regression model will be carried out to determine which risk factors are associated with “time-to-return visit”. Proposed factors will include age, sex, race, diabetes, hyperlipidemia, hypertension, active smoking and smoking history, family

history of premature heart disease, obesity, and the number of cardiac risk factors present. In addition we will consider adding whether the admission was surgical or medical, and the MS or AP DRG case weight as a measure of severity.

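### The Aim 3 return-visit model lists the individual cardiac risk factors and also their undefined count, so those effects cannot be separated, and it has at least 11 terms with no selection rule or penalisation

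*Combined protocol and SAP*

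**What the plan says.** For Aim 3, section 14.2 states that "a survival analysis regression model will be carried out to determine which risk factors are associated with" time to return visit. The type of survival model is not named.

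The covariate list begins "Proposed factors will include age, sex, race, diabetes, hyperlipidemia, hypertension, active smoking and smoking history", goes on to family history, and ends "obesity, and the number of cardiac risk factors present". Two further covariates are left open: "In addition we will consider adding whether the admission was surgical or medical, and the MS or AP DRG case weight". The paragraph appears twice in section 14.2 with the same list.

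The analysis set is return visits "in patients who had no ICA test or a negative ICA test result". On the outcome: "Return visit is defined as patients who return for unplanned cardiac care", which takes in emergency room visits and emergency admissions as well as urgent revascularisation and myocardial infarction.

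The nearest thing to a definition of a cardiac risk factor is the history-taking text in section 7.4, which gives an open list: "smoking, family history of heart disease, hyperlipidemia, diabetes, hypertension". All five are also separate covariates in Aim 3. Neither section says what the count contains, how any covariate is coded, how covariates would be selected, or how many return visits are expected.

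**The concern.** A count formed by adding up binary factors carries no information beyond those factors. With both in one regression, the model cannot tell the effect of having diabetes from the effect of having one more risk factor. Some term must be removed before the model can be fitted. The reported hazard ratios for the factors and the count then reflect that choice as well as the data. Aim 3 exists to identify factors associated with return visits, so this bears directly on its answer.

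The second issue is the number of terms against the likely number of events. A 90-day unplanned return may be uncommon in outpatients from whom the ICA-positive patients have been removed. The plan neither estimates that number nor limits the model. With few events per term, unpenalised estimates are unstable, and a factor can look important or unimportant by chance.

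**Working it through.** **1. Terms.** With race as one degree of freedom, the listed covariates are age, sex, race, diabetes, hyperlipidemia, hypertension, active smoking, smoking history, family history, obesity and the count: 11 terms. The two optional covariates make 13. A race variable with more categories adds more.

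**2. What exact collinearity does.** Suppose the count is C = ΣX_j over the listed factors. The linear predictor contains Σβ_jX_j + γC = Σ(β_j + γ)X_j. Only the sums θ_j = β_j + γ can be estimated.
- Drop C: each X_j has coefficient θ_j.
- Drop X_k and keep C: C has coefficient θ_k, and every other component has θ_j − θ_k.

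The fitted model is the same either way. Coefficients of terms outside the set do not change, but those of the count and its components do. A larger sample does not help.

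**3. Does it depend on the definition of the count?** Simulated designs had 472 patients, the 11 terms and an intercept (12 columns). Assumed prevalences were diabetes 20%, hyperlipidemia 50%, hypertension 50%, family history 30%, obesity 30%, former smoking 30% and active smoking 15%. The overlapping-smoking row instead used a separate past-smoking indicator at 40%.

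| Definition of the count | Rank | Variance inflation of the count |
|---|---|---|
| Sum of six factors, any smoking | 11 of 12 | infinite |
| Sum of the five in section 7.4 | 11 of 12 | infinite |
| Sum of six, current smoking only | 11 of 12 | infinite |
| Sum, smoking as either of two overlapping indicators | 12 of 12 | about 38 |
| Sum of six plus an age/sex threshold | 12 of 12 | about 17 |
| Dichotomised at 3 or more | 12 of 12 | about 3 |

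The rank results for the simple sums follow from the algebra. The finite inflation figures depend on the assumed prevalences.

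**4. Size of the Aim 3 set.** The plan gives no calculation for Aim 3, so its section 14.1 figures are used. Those reproduce:
- n = [1.96√(0.14×0.86) + 0.8416√(0.06×0.94)]² / 0.08² = 120.99, i.e. 121 ICA patients
- 121/(0.60×0.35) = 576.2, i.e. 576 completers

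Aim 3 removes the ICA-positive patients:
- 14% of ICA negative: 576 − 121×0.86 = 472
- 6% of ICA negative: 576 − 121×0.94 = 462

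Starting from the 572 in the study summary changes this little (459 to 469).

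**5. Events per term.** The return rate is an assumption throughout.

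| Assumed 90-day rate | Events (462 to 472 patients) | Events per term, 11 terms |
|---|---|---|
| 1% | 4.6 to 4.7 | 0.4 |
| 5% | 23.1 to 23.6 | 2.1 |
| 10% | 46.2 to 47.2 | 4.2 to 4.3 |
| 20% | 92.5 to 94.4 | 8.4 to 8.6 |

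Ten events per term, which is a convention and not a threshold, would need 110 events: 110/472 = 23%. Removing only the count leaves 10 terms and, for 5 to 24 events, 0.5 to 2.4 per term.

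**6. Precision.** By Schoenfeld's formula, the hazard ratio detectable with 80% power at two-sided 0.05 for one binary factor of prevalence p with d events is exp{2.80/√[d p(1−p)]}. For p = 50% and 30% respectively:
- 5 events: about 12 and 15
- 24 events: 3.1 and 3.5
- 47 events: 2.3 and 2.4
- 94 events: 1.8 and 1.9

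These values ignore correlation with other covariates, which would make them worse.

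**The case against.** The count is undefined, so exact collinearity is conditional. A count that includes an age/sex threshold, or treats smoking as either of two overlapping indicators, gives a full-rank design, and a dichotomised count is only mildly collinear. This stands as a limit on the claim. It does not remove the problem: the plan speaks of a number, the factors named in section 7.4 are all in the model, and a linear count that adds an age/sex threshold or overlapping smoking indicators is still strongly collinear.

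The list is headed as proposed factors and could be read as candidates from which a smaller model is chosen. That is a fair reading, but no selection rule is given, so the choice would be made after seeing the data.

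A reader might infer that every hazard ratio in the model changes meaning. That is not so: under exact collinearity only the count and its components are affected, and if the count is the term removed, the factor hazard ratios keep their ordinary interpretation.

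A reader might also take 5 to 24 as the number of events to expect. The documents give no rate. The outcome is broad and includes emergency room visits, so the rate could be higher, which is why 10% and 20% are shown.

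Finally, Aim 3 is not among the primary or secondary endpoints in sections 6.2 and 6.3, and the sample size does not rest on it. This stands and limits the priority.

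**Conclusion.** The point holds in a conditional form. If the count is the sum of listed factors, which section 7.4 makes the natural reading, its effect and those of its components are not separately identifiable at any sample size. With an age/sex threshold added, they are separable only weakly, with variance inflation of about 17 under the assumed prevalences.

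Separately, 11 or more unpenalised terms are too many for the likely information. Events per term are about 0.4 to 2.1 at an assumed 1% to 5% return rate, and stay below ten unless about 23% of patients return within 90 days. It would be too strong to say that few events make the effects impossible to estimate. They make the estimates unstable and imprecise; strict non-identifiability comes only from the exact collinearity.

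The result rests on the section 14.1 proportions, race as one degree of freedom, and assumed return rates. It is a lower-priority correction to an aim outside the listed endpoints.

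**What to change.** In both copies of the Aim 3 paragraph in section 14.2:

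- State that a given model contains either the individual factors or their count, never both.
- Because the aim is to identify factors, keep the individual factors, fit them with a penalised survival model (for example Firth's method), and label the results exploratory.
- Define the count by listing its components and how smoking is coded, and report it in a separate model adjusted for age and sex.

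An assumed return rate and the expected number of events, stated alongside, would let readers judge the precision.

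The cost is a change of wording, one additional model, and factor estimates that are shrunken. Penalisation limits instability but adds no information: near 5 events, either model would remain very imprecise. No data collection or sample size changes.

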14.3 Subject Population(s) for Analysis

This is not a randomized trial. Data for all subjects who enroll in the study will be subject to analysis, with appropriate adjustments for those who were unable to finish any part of the study.

15 Safety and Adverse Events

15.1 Definitions

Adverse Event

An **adverse event** (AE) is any symptom, sign, illness or experience that develops or worsens in severity during the course of the study, as a result of study activities. Intercurrent illnesses or injuries will be regarded as adverse events. Abnormal results of diagnostic procedures are considered to be adverse events if the abnormality:

- results in study withdrawal
- is associated with a serious adverse event
- is associated with clinical signs or symptoms
- leads to additional treatment or to further diagnostic tests
- is considered by the investigator to be of clinical significance

Serious Adverse Event

Adverse events are classified as serious or non-serious. A **serious adverse event** is any AE that is:

- fatal
- life-threatening
- requires or prolongs hospital stay
- results in persistent or significant disability or incapacity
- an important medical event

Important medical events are those that may not be immediately life threatening, but are clearly of major clinical significance. They may jeopardize the subject, and may require intervention to prevent one of the other serious outcomes noted above. For example, drug overdose or abuse, a seizure that did not result in in-patient hospitalization, or intensive treatment of bronchospasm in an emergency department would typically be considered serious.

All adverse events that do not meet any of the criteria for serious will be regarded as **non-serious adverse events**.

Adverse Event Reporting Period

The study period during which adverse events must be reported will be defined as the period from the initiation of any study procedures to the end of the study treatment follow-up. For this study, the study treatment follow-up is defined as 90 days following the last administration of study treatment.

Preexisting Condition

A preexisting condition is one that is present at the start of the study. Preexisting conditions will be recorded as an adverse event if the errors in diagnosis cause less than optimal treatment decisions.

General Physical Examination Findings

At screening, any clinically significant abnormality will be recorded as a preexisting condition. At the end of the study, any new clinically significant findings/abnormalities that were not diagnosed through the study protocol will meet the definition of an adverse event and will also be recorded and documented as an adverse event.

Post-study Adverse Event

All unresolved adverse events should be followed by the investigator until the events are resolved, the subject is lost to follow-up, or the adverse event is otherwise explained.

Hospitalization, Prolonged Hospitalization or Surgery

Any adverse event that results in hospitalization or prolonged hospitalization will be documented and reported as a serious adverse event. Any condition responsible for surgery will be documented as an adverse event if the condition meets the criteria for an adverse event.

Neither the condition, hospitalization, prolonged hospitalization, nor surgery will be reported as an adverse event in the following circumstances:

- Hospitalization or prolonged hospitalization for diagnostic or elective surgical procedures for a preexisting condition. Surgery will **not** be reported as an outcome of an adverse event if the purpose of the surgery was elective or diagnostic and the outcome was uneventful.
- Hospitalization or prolonged hospitalization for therapy of the target disease of the study, unless it is the result of inaccurate diagnostic information provided in the study.

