15.2 Recording of Adverse Events

At the follow-up contact with the subject, the study coordinator will seek information on adverse events by specific questioning and, as appropriate, by referral to a study coordinator for examination. Information on all adverse events should be recorded immediately in the source document, and also in the appropriate adverse event module of the case report form (CRF). All clearly related signs, symptoms, and abnormal diagnostic procedures results should be recorded in the source document, though should be grouped under one diagnosis.

All adverse events occurring during the study period will be recorded. The clinical course of each event should be followed until resolution, stabilization, or until it has been determined that the study treatment or participation is not the cause. Serious adverse events that are still ongoing at the end of the study period will be followed up to determine the final outcome. Any serious

adverse event that occurs after the study period and is considered to be possibly related to the study treatment or study participation will be recorded and reported immediately.

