15.7.1 Data and Safety Monitoring Plan

[name]. will conduct data safety monitoring for the study.

His role as Director of the Cardiac Catheterization program at Lenox Hill Hospital makes him the most appropriate person to review the study safety, because he will have the most complete information on the cardiovascular condition of the patient, and the patients response to invasive ICA, the primary study activity that has potential to influence patient safety.

The expected types of events that will be monitored include major adverse cardiac events resulting from any Cardiac Catheterization, Percutaneous Coronary Intervention, or Coronary Artery Bypass Graft in a patient who, if not enrolled in the study, would not have received Cardiac Cath or invasive treatments. In addition, the monitor will review any medical complications for these subjects. The study coordinator will refer all patients who received Cardiac Cath, who would not have otherwise have received it if not part of the study. The monitor will review whether adverse events were the result of the study activity or related to procedures provided as part of standard of care, and whether safety policies and procedures were followed within one week of the all referrals. The monitor will present any recommendations for changes to the study resulting from the review to the study PI.

The monitor will conduct reviews as near as possible to the time the event was identified and always within a month of the identification of the event.

We do not expect to need to alter or interrupt the study design, because of the very low risk nature of the study. However, any unexpected safety events related to the study design will be carefully reviewed by the Safety Monitor and the study PI and reported to the IRB and Hospital quality assurance. If improvement in patient safety can be made by changing the design, immediate consideration will be given to the prospective change.

There are no issues with toxicity in this study.

If the study should be temporarily suspended, we will report this to the IRB, Clinical trials.gov, and to HeartFlow.

16 Data Handling and Record Keeping

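### The adverse event definition in section 15.1 requires study causation, which conflicts with the rules in 15.1, 15.2 and 15.7.1 that record events first and judge cause afterwards

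*Combined protocol and SAP*

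**What the plan says.** The combined protocol and SAP deals with adverse events in section 15.

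- **15.1, first sentence.** The definition of an AE reads: "any symptom, sign, illness or experience that develops or worsens in severity during the course of the study, as a result of study activities".
- **15.1, next sentence.** "Intercurrent illnesses or injuries will be regarded as adverse events". No causal link is asked for.
- **15.1, end-of-study findings.** The rule here says that "any new clinically significant findings/abnormalities that were not diagnosed through the study protocol will meet the definition of an adverse event". Again no causal link is asked for.
- **15.1, serious events.** A serious adverse event (SAE) "is any AE that is" fatal, life-threatening or otherwise serious on the listed criteria. Section 15.3.2 sends SAE reports to the IRB.
- **15.2.** All AEs in the study period are recorded. Each is followed to resolution, to stabilization, or "until it has been determined that the study treatment or participation is not the cause". The study coordinator questions the patient at follow-up and, "as appropriate, by referral to a study coordinator for examination", may send the patient on.
- **15.7.1.** "The monitor will review whether adverse events were the result of the study activity or related to procedures provided as part of standard of care". The coordinator refers to the monitor those patients who were catheterized only because they were in the study.

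**The concern.** If an event must be caused by the study to be an AE, someone has to judge cause before the event enters the record. The later steps that judge cause would then see only events already accepted as study-caused, and would have little left to decide. The same condition passes to SAEs, because they are a subset of AEs.

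What is at stake is how the safety record can be read. With a causal condition at entry, a low AE count could reflect either few harms or a narrow reading of the definition, and the count alone could not tell these apart. The question matters most for invasive coronary angiography (ICA). Section 9 describes most referrals to it as standard of care, and section 12 recognizes only one kind of research-related injury: harm from a catheterization that the patient might not otherwise have had. Staff who carried that narrow view over to the AE definition could treat a complication of a standard-of-care ICA as outside it.

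**Working it through.** This is a check of text against text. The documents give no AE rate, AE count or safety sample size, so there is no planned figure to reproduce.

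**Step 1: apply the 15.1 definition literally and test each neighbouring rule.**

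| Rule | Effect if only study-caused events are AEs |
|---|---|
| 15.1, intercurrent illness or injury counts | Contradicted: such illness is generally not caused by the study |
| 15.1, new end-of-study findings count | Contradicted: no causal link is required there |
| 15.2, follow-up may end once the study is ruled out as cause | Empty: an AE could never be found unrelated |
| 15.2, SAEs after the study period are reported if possibly related | Redundant: relatedness would already be part of being an SAE |
| 15.7.1, monitor separates study activity from standard of care | Nearly empty: the separation would already have been made |

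Two rules are contradicted and three lose most or all of their content. The natural reading of the rest of section 15 is that events are recorded whatever their cause, and that cause is assessed later. The definition is the sentence that does not fit.

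**Step 2: follow the definition into serious events.** An SAE is an AE that meets a seriousness criterion. Any condition on AEs is therefore a condition on SAEs, and on what goes to the IRB under 15.3.2.

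**Step 3: see who does what.** The coordinator elicits events (15.2). The investigator follows unresolved events (15.1). The principal investigator is responsible for assessing and reporting AEs (15.6). The monitor reviews attribution (15.7.1). Nobody is expressly assigned to decide cause at the point of entry, although the definition would need someone to do so. The referral in 15.2 runs from a coordinator to a coordinator, so it names no clinician at that step.

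**Step 4: can the effect be sized?** The nearest figure is the number of ICAs expected in 14.1: 576 × 0.60 × 0.35 = 120.96, about 121. If a complication rate of 1% to 3% were assumed (the documents give none), the total would be 121 × 0.01 = 1.21 to 121 × 0.03 = 3.63 complications over all ICAs. To turn that into unrecorded events needs two further figures: the share of ICAs regarded as standard of care, and the share of their complications that staff would leave out. The documents give neither, and each could lie anywhere from 0 to 1. The result runs from 0 to about 3.6 under that assumption, which is not an estimate.

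**The case against.** A reader might infer three stronger things, and the documents support none of them.

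**That the coordinator pre-screens causality and no physician sees the event.** No section gives the coordinator this task. Section 15.2 has the coordinator seek information and has all AEs recorded at once; 15.1, 15.6 and 15.7.1 give the investigator, the principal investigator and the monitor their own roles. The coordinator-to-coordinator referral reads like a drafting slip. The coordinator does select catheterized patients for the monitor in 15.7.1, but that test concerns why the catheterization was done, not what caused an event.

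**That complications of standard-of-care ICAs fall outside the definition.** Section 15.7.1 itself describes ICA as the main study activity that could affect patient safety. It also has the monitor identify events due to standard-of-care procedures, which presupposes that such events are recorded. Section 12 is narrower, but it concerns research injury and liability.

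**That events are lost, at a rate of one to four.** The rules on intercurrent illness, new findings and recording all AEs point towards capture. Section 8.6 also has a 90-to-120-day interview on follow-up care with no causal filter. The 90-day return visit in 14.2 likewise takes unplanned cardiac care whatever its cause, although Aim 3 covers only patients with no ICA or a negative one.

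It can also be said that section 14 plans no analysis of AE counts, and that the low-risk statement in 15.5 is a premise drawn from standard-of-care use. Both are right, and they limit the consequence to safety reporting. They do not remove the contradiction: staff cannot follow the definition and the surrounding rules together.

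**Conclusion.** The point holds as an internal inconsistency in the safety rules. The causal condition in the AE definition cannot be applied together with two other rules in 15.1, the follow-up rule in 15.2 or the monitor's task in 15.7.1, and it reaches SAE reporting through the way SAEs are defined. Taken literally, it would permit events judged unrelated to be omitted before the investigator or monitor reviews them, possibly including complications of standard-of-care ICAs.

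That is a risk created by the wording. The documents do not establish that events will be omitted, who would omit them, or how many, and no number should be attached. The conclusion rests only on a plain reading of section 15. The sample size and the primary analysis are not affected. The plan should still be corrected, because the change is small and removes doubt about what the safety record contains.

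**What to change.** 1. **15.1:** delete the causal phrase at the end of the AE definition, so that an event in the reporting period is an AE whatever its cause. Keep the hospitalization and surgery exceptions already stated in 15.1, so that the edit does not create a new conflict.
2. **Case report form:** add a separate relatedness field, completed by the investigator after the event has been recorded.
3. **15.2:** replace the circular referral with referral to a study cardiologist or investigator. Section 5 already lists six attending cardiologists on the team.
4. **15.7.1:** reconcile the rule on which catheterized patients are referred to the monitor with the monitor's task of separating study-related events from standard-of-care events. The edit to 15.1 does not settle this, because the referral rule limits what the monitor sees whatever the AE definition says.

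The cost is a few wording changes and one extra field, with no new staff. The downside is that more unrelated events will be logged and assessed.
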